**Table 5: Vital Signs Thresholds**

Heart Rate (bpm)	Systolic Blood Pressure (mmHg)	Diastolic Blood Pressure (mmHg)
< 40	< 85	< 45
> 110	> 160	> 100

## 8.6. 12-Lead Safety ECGs

ECG summaries will include summary statistics for observed values and changes from baseline. Heart rate and the following intervals will be included: PR, QRS, QT, and QTcF. A listing of 12-lead safety ECG data collected will be provided. A separate listing of data for subjects with postbaseline values of QTcF  $\geq 500$  msec or a QTcF increase from baseline  $> 60$  msec will also be provided.

In addition, QTcF (msec) will be summarized by the following categories: Normal (males  $< 430$ , females  $< 450$ ), Borderline (males  $[\geq 430, < 450]$ , females  $[\geq 450, < 470]$ ), and Prolonged (males  $\geq 450$ , females  $\geq 470$ ).

### Investigator Assessment of ECGs

The investigator’s assessment of ECGs as normal, abnormal and clinically significant, or abnormal but not clinically significant will be summarized for baseline and for each visit.

### Categorical ECG Summary

The number of subjects with absolute ECG values and changes from baseline in the ranges shown in [Table 6](#) will be presented by visit.

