**Table 4: Electrocardiogram Test Outlier Thresholds**

Heart Rate (bpm)	Heart Rate Change From Baseline (bpm)	PR Interval (msec)	PR Percentage Change From Baseline (%)	QRS Interval (msec)	QT c F (msec)	QT c F Change From Baseline (msec)
>120	≥20	≥200	≥15	≥120	Males:	≤30
>130	≥30	≥220	≥25		<430	>30, ≤60
					≥430	>60
					≥450	
					≥470	
					≥480	
					≥500	
					Females:	
					<450	
					≥450	
					≥470	
					≥480	
					≥500	

Treatment emergent ECG abnormalities are defined as those not present at baseline, or those that worsened after treatment, e.g., borderline at baseline but were prolonged after treatment. QTcF {and QTcB} will also be summarized by the following categories, Normal (males <430, females <450), Borderline (males (≥430, <450); females (≥450, <470)) and Prolonged (males ≥450, females ≥470).

When multiple values exist for the same nominal time point (e.g., triplicate reading), the average of the readings taken for ECG parameters will be used in the data analysis, including the outlier analysis stated below.

Subjects without post-baseline measurement for a given treatment period will be excluded from the summary statistic (e.g., denominator of the summary statistic) for that time point.

All recorded values for the ECG parameters will be presented in a by-subject listing. A separate listing of subjects with values of QTcF > 500 msec or an increase > 60 msec will be provided, as necessary.

Cumulative distribution plots will be provided for maximum change in QTcF by day.

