#### 8.4. Laboratory Data

Laboratory data hematology and serum chemistry summaries will include summary statistics for observed values and for changes from baseline at each postdose visit. In addition, changes from baseline for each visit relative to normal ranges (e.g., shifts from normal to abnormal high/low) will be summarized in shift tables for hematology and serum chemistry test results. (Urinalysis data will be listed only.)

Listings will flag laboratory values that are outside the normal range.

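### SAP 8.6 never turns the protocol's definition of a treatment-emergent ECG abnormality into a count: its ECG category summaries are not crossed with each subject's own baseline

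*SAP*

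**What the plan says.** **Protocol 8.5.6**, below Table 4, gives the definition: "Treatment emergent ECG abnormalities are defined as those not present at baseline, or those that worsened after treatment". Its example is a change of category, "borderline at baseline but were prolonged after treatment", and the QTcF cut-offs for Normal, Borderline and Prolonged follow.

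**Protocol 8.5** keeps categorical data from unscheduled times, with ECG finding categories as its example, out of the by-time-point summaries. It puts them into summaries covering the entire treatment period.

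**SAP 8.6** plans three categorical ECG summaries:
- by visit, "The number of subjects with absolute ECG values and changes from baseline in the ranges shown in" Table 6;
- "In addition, QTcF (msec) will be summarized by the following categories: Normal", Borderline and Prolonged, with the protocol's cut-offs and no stated time point;
- the investigator's three-way assessment, which "will be summarized for baseline and for each visit".

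Table 6 has change-from-baseline columns for heart rate, PR (percent) and QTcF, and none for QRS. SAP 8.6 also plans summary statistics of values and changes for heart rate, PR, QRS, QT and QTcF, a listing of the safety ECG data, and a separate listing for QTcF of at least 500 msec or an increase above 60 msec.

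**SAP 6 and 6.3.5** limit summaries, unless noted otherwise, to data inside the analysis windows, whatever the visit label. A redacted stretch follows that rule in SAP 6.

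**SAP 8.4** plans for hematology and chemistry that "changes from baseline for each visit relative to normal ranges (e.g., shifts from normal to abnormal high/low) will be summarized in shift tables". No ECG output has this form.

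**The concern.** Resting ECG is one of the primary safety endpoints, and cardiac arrhythmia is an adverse event of special interest. The study has one arm, so a subject's own baseline is the within-study reference. Separate counts at baseline and at later visits do not say how many subjects changed category. They can also move merely because subjects leave, or stay level while some subjects improve and others worsen.

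At stake is whether the report can state how many subjects had an ECG abnormality that was new or worse than at baseline, which is how the protocol defines treatment-emergent. Protocol 8.1 says changes to protocol-specified analyses will be pre-specified in the SAP. SAP 8.6 neither applies the definition nor says that it is set aside.

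**Working it through.** The documents state no figure on this point, so there is none to reproduce. The check has four steps.

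**1. Does any planned count use the subject's baseline category?** From the text above, none does. The absolute columns of Table 6 use the post-baseline value alone. The change columns use the difference alone and are tabulated separately. The investigator assessment is given as one distribution at baseline and one at each visit.

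**2. Can the planned cells separate new from pre-existing?** Hypothetical subjects, classified by Table 6 and by the protocol definition:

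| Subject (msec) | Absolute cells | Change cell | New or worse? |
|---|---|---|---|
| Male QTcF 455 to 455 | ≥430, ≥450 | 0, so ≤30 | no |
| Male QTcF 440 to 455 | ≥430, ≥450 | 15, so ≤30 | yes, Borderline to Prolonged |
| Female QTcF 475 to 475 | ≥450, ≥470 | 0, so ≤30 | no |
| Female QTcF 460 to 475 | ≥450, ≥470 | 15, so ≤30 | yes, Borderline to Prolonged |
| PR 205 to 205 | ≥200 | 0%, below 15% | no |
| PR 195 to 205 | ≥200 | 10/195 = 5.1%, below 15% | yes, crosses 200 |
| QRS 125 to 125 | ≥120 | no column | no |
| QRS 115 to 125 | ≥120 | no column | yes, crosses 120 |

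In each pair the planned cells are identical and the protocol status differs. A larger rise does show: a male going from 425 to 456 msec has a change of 31 and enters the >30 to ≤60 row. Even then, nothing links that row to the subject's absolute category.

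**3. How far can separate counts mislead?** These are illustrations. The 110 is the number enrolled (SAP 2). The other inputs are assumptions, as is the supposition that all 110 have baseline and post-baseline ECGs.

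- Suppose 15 are prolonged at baseline. If all 15 stay prolonged, the counts are 15/110 = 13.6% before and after, with 0 new. If 5 normalise and 5 others become prolonged, the later count is 15 − 5 + 5 = 15, again 13.6%. The new cases are now 5/110 = 4.5% of subjects, or 5/(110 − 15) = 5/95 = 5.3% of those not prolonged at baseline. The planned counts are the same in both cases.
- More generally, let p be baseline prevalence and r new occurrence among the rest, with pre-existing cases persisting. The count is 110p + 110(1 − p)r, and the pre-existing share is p / [p + (1 − p)r].

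| p | r | Count | New | Pre-existing share |
|---|---|---|---|---|
| 5% | 2% | 7.6 | 2.1 | 72% |
| 5% | 10% | 16.0 | 10.5 | 34% |
| 30% | 2% | 34.5 | 1.5 | 96% |
| 30% | 10% | 40.7 | 7.7 | 81% |

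**4. Is there a whole-period summary?** The readable SAP 8.6 has none. SAP Table 4 has seven windows of 15 days, so 7 × 15 = 105 of Days 1 to 189 are covered and 84 (44%) are not, for example Days 50 to 62 and 78 to 90. On the readable text, an unscheduled or early-termination ECG on an uncovered day appears only in a listing. Protocol 8.5 would put its category into a whole-period summary.

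**The case against.** The case on the other side is substantial, and most of it stands as a limit on the point.

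- **No named table was dropped.** A reader might infer that the SAP deleted a protocol-specified ECG table. The readable protocol does not support that: it defines the term but attaches no count or shift table to it, and SAP Table 6 repeats the thresholds of Protocol Table 4. What remains is a definition that was never put into operation.
- **The SAP is not purely absolute.** It has change categories for heart rate, PR and QTcF, continuous change for QRS, and a listing of large QTcF values and increases. This stands, but step 2 shows that those outputs do not count newly crossed thresholds.
- **The laboratory contrast proves little.** Protocol 8.5.4 itself asks for laboratory changes relative to normal ranges and has no ECG equivalent. The laboratory shift tables show only that the format is already in use.
- **New events are separated elsewhere.** A reader might infer that pre-existing abnormalities are counted as new throughout the safety report. They are not. Protocol 7.2 has clinically significant or symptomatic ECG abnormalities recorded as AEs if they meet the AE definition, Protocol 7.1.1 sends conditions with onset before the first dose to medical history, and SAP 8.1 and 8.1.1 summarize treatment-emergent AEs and AESIs. The gap concerns ECG measurements and categories that do not become AEs.
- **There are few ECG visits.** Post-baseline ECGs are scheduled only at Weeks 10 and 26 and at early termination up to Week 26. With the listings, the status of up to 110 subjects could be worked out by hand. That is true, but no planned table would report it.
- **Baseline may not be drug-free.** It is Study 0170 Visit 9 (SAP 6.2), and SAP 7.5 refers to a randomized withdrawal period in that study. A shift from this baseline therefore does not by itself show emergence on drug. This belongs in the table's footnote.

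**Conclusion.** The point holds in a limited form. Protocol 8.5.6 says what makes an ECG abnormality treatment-emergent, and no table in the readable SAP 8.6 counts it. The gap covers the absolute-threshold counts, the QTcF category summary and the investigator assessment. The missing whole-period categorical summary is part of the same gap.

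Its numerical size cannot be known from the documents. The 34% to 96% range and the contrast of 15/110 with 5/110 or 5/95 rest entirely on assumed prevalences and on all 110 subjects having usable ECGs. That the planned cells cannot separate the pairs in step 2 rests on no assumption about prevalence.

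The consequence is modest: a descriptive single-arm safety summary with no hypothesis test. The change is still worth making, because it uses a definition already in the protocol and data already collected. The conclusion also assumes that no redacted text supplies the missing summary; no redaction is visible in SAP 8.6.

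**What to change.** Add to SAP 8.6:

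1. A shift table of baseline by worst post-baseline category over the treatment period, including unscheduled and early-termination ECGs whether or not they fall in an analysis window. Use these categories:
   - QTcF: Normal, Borderline and Prolonged, with Prolonged split at the existing 480 and 500 msec thresholds. A male going from 455 to 505 msec then counts as worsened.
   - PR: <200, 200 to <220, ≥220 msec.
   - QRS: <120, ≥120 msec.
   - Investigator assessment: the three existing levels.
2. The number and percentage of subjects with a new or worsened abnormality under Protocol 8.5.6. The denominator is subjects with a baseline and at least one post-baseline ECG. Do not restrict it to those outside the worst category at baseline, since that would drop subjects who worsen within it.
3. A footnote that baseline is Study 0170 Visit 9, after a randomized withdrawal period, and is not necessarily drug-free.
4. A sentence saying how worsening inside the top PR or QRS category is treated, since a category shift cannot show it.

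If the sponsor prefers not to use the definition, the SAP should say so and give the reason. The cost is SAP wording and one or two extra descriptive tables; no new data are needed.

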### **6.3.10. Early Termination Up to Week 26**

Subjects terminating the study prior to Week 26 will complete all of the following procedures.

1. Review concomitant medications

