#### 6.4.3.9.4. Unscheduled Visit

All sites are allowed, at Investigator discretion, to conduct either in clinic or remote unscheduled visit(s) for subject safety or unexpected subject medical needs outside of the regular visit schedule. In this case, unscheduled visits are not considered protocol deviations and the Investigator is not required to obtain pre-approval from the Sponsor. Data collected during these visits may include any protocol-specified assessments which will be captured in the clinical database.

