## **6. CONSIDERATIONS FOR DATA ANALYSES AND HANDLING**

All data from scheduled and unscheduled visits will be presented in the subject listings.

However, unless noted otherwise, only data from visits (scheduled or unscheduled) that fall within the analysis windows will be included in summaries, statistical analyses, and calculation of derived variables. [REDACTED]

Analyses and tabulations will be prepared using [REDACTED]

Summary tables and listings will be prepared according to ICH Guideline E3 and will include a “footer” providing explanatory notes.

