### **6.3.5. Visit Windows**

All assessments will be summarized using analysis windows. The term “out of window” will be applied to assessments that are outside the analysis windows, regardless of the visit label associated with the assessment in the EDC system.

The following visit windows will be used in the summarization of clinical data:

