#### 6.3.6. Multiple Assessments

In general, if multiple valid observations exist at a visit or collection time point, the record(s) to be included in the summary and analyses will be chosen based on the following:

- The record closest to the nominal time

If 2 records are equidistant or distance cannot be determined:

- The later record

If there are 2 or more records with the same date/time:

- The average (generally applies to assessments done in triplicate)

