### **8.1.1. Adverse Events of Special Interest**

An AE of special interest (AESI) is one of scientific and medical interest specific to understanding the investigational product and may require close monitoring and rapid communication by the investigator to the sponsor. The following are the AESIs defined for the study:

- Supine Hypertension
- Myocardial Infarction
- Cerebrovascular Accident
- Cardiac Arrhythmia
- Congestive Heart Failure
- Convulsion

The incidence of treatment-emergent AESIs will be summarized, overall (any AESI) and by system organ class and preferred term. A listing of AESIs will be provided.

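### ECG threshold counts are given by visit and from in-window data only, so no visible table shows how many subjects ever crossed a threshold, and off-window Early Termination and unscheduled ECGs reach no summary

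*SAP*

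**What the plan says.** Resting ECG is one of the primary safety endpoints (SAP 3.2.1). SAP 8.6, Categorical ECG Summary, states that "The number of subjects with absolute ECG values and changes from baseline in the ranges shown in" Table 6 will be presented by visit. The investigator's ECG assessment is likewise summarised at baseline and each visit. The Normal/Borderline/Prolonged QTcF summary in 8.6 has no stated time basis.

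Three general rules decide which ECGs can enter those tables:

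- SAP 6: unless noted otherwise, "only data from visits (scheduled or unscheduled) that fall within the analysis windows will be included in summaries". A redacted span follows this rule.
- SAP 6.3.5: "All assessments will be summarized using analysis windows", and a record counts as out of window by its date, whatever visit label it carries in the database. Table 4 has seven windows, the last ending on Day 189, and no row for Early Termination or for any time on treatment.
- SAP 6.3.6: where a visit has several valid records, the one kept is "The record closest to the nominal time", not the worst.

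The protocol collects ECGs that these rules can exclude. Section 6.3.10 says "Subjects terminating the study prior to Week 26 will complete all of the following procedures", and a triplicate ECG is on that list. Section 6.4.3.9.4 allows unscheduled visits: "Data collected during these visits may include any protocol-specified assessments which will be captured in the clinical database".

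Protocol 8.5 keeps unscheduled quantitative data out of summaries. It puts unscheduled categorical data, with ECG finding categories as its example, into summaries covering the whole treatment period. Protocol 8.5.6 also defines treatment-emergent ECG abnormalities and promises cumulative plots of maximum QTcF change. None of these whole-period or treatment-emergent elements appears in the visible SAP 8.6.

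**The concern.** The natural safety question for a threshold is how many subjects crossed it at least once on treatment, out of how many with a post-baseline ECG. By-visit counts do not answer it, because the same subject may appear at one visit or at several.

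The window rule adds a second problem. Post-baseline ECGs are scheduled only at Weeks 10 and 26, plus Early Termination up to Week 26. A subject who left before Week 10 may have a single post-baseline ECG, the Early Termination one. If its date falls between windows, that subject drops out of both numerator and denominator. Both this study and its feeder were terminated early, so such subjects may not be rare. A termination visit or a symptom-prompted visit is also where an abnormal tracing might be expected.

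**Working it through.** The plan gives no figure to reproduce for this point, so the check is a count of days followed by an illustration in subjects.

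**Days outside every window (SAP Table 4).** The windows are Days 7–21, 35–49, 63–77, 91–105, 119–133, 147–161 and 175–189.

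- Covered: 7 × 15 = 105 days.
- Uncovered in Days 1–189: 189 − 105 = 84 days; 84/189 = 44.4%.
- The gaps are Days 1–6, 22–34, 50–62, 78–90, 106–118, 134–146 and 162–174: 6 + 6 × 13 = 84.

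These are days, not ECGs. Scheduled Week 10 and Week 26 ECGs taken within their ±7 days fall inside the windows and are summarised. The exposed records are Early Termination and unscheduled ECGs on the 84 days, unscheduled ECGs after Day 189, and any second in-window ECG displaced under SAP 6.3.6.

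**Subjects affected.** From the documents: 110 enrolled (SAP 2). Assumed, because the documents do not say: 20% to 60% of the 110 (22 to 66 subjects) stop before Day 175, stop days are spread evenly over Days 1–174, and the Early Termination ECG is taken on the stop day.

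| Situation | Share of stop days | 22 stop | 66 stop |
|---|---|---|---|
| Only post-baseline ECG lost: stop on an uncovered day in Days 1–62 (6 + 13 + 13 = 32) | 32/174 = 18.4% | 4.0 (3.7% of 110) | 12.1 (11.0% of 110) |
| Same, if ECGs are tabulated only at Weeks 10 and 26 (all of Days 1–62) | 62/174 = 35.6% | 7.8 (7.1%) | 23.5 (21.4%) |
| Week 10 ECG kept, Early Termination ECG lost: uncovered days in 78–174 (4 × 13 = 52) | 52/174 = 29.9% | 6.6 | 19.7 |
| Same, if ECGs are tabulated only at Weeks 10 and 26 (all of Days 78–174, 97 days) | 97/174 = 55.7% | 12.3 | 36.8 |

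**What by-visit counts leave open.** Suppose 3 subjects cross a threshold at Week 10 and 3 at Week 26. The number ever affected is anywhere from 3 (same subjects) to 6 (different subjects), that is 3/110 = 2.7% to 6/110 = 5.5%.

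More generally, let all 110 have both ECGs and let a proportion p cross at each visit. The ever-crossed count runs from 110p, if the same subjects cross both times, to 110 × [1 − (1 − p)²], if the visits are independent:

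- p = 2%: 2.2 to 4.4 subjects
- p = 5%: 5.5 to 10.7
- p = 10%: 11.0 to 20.9

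The values of p are illustrative.

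**Is there an exception for ECGs?** None is visible in SAP 8.6. The SAP does write a whole-interval count where it wants one: section 8.7 counts subjects with at least one fall from Day 1 to Day 189.

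**The case against.** **Redaction.** The window rule allows exceptions and is followed by blacked-out text, which could contain one for Early Termination or any-time ECG counts. This cannot be excluded, so the point applies to the visible SAP only.

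**QTcF categories.** The Normal/Borderline/Prolonged summary is not labelled by visit and might be meant per subject. But the window rules cover it by default, and nothing defines it as a worst or any-time value. For that table the specification is at best unclear.

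**Protocol 8.5.** ECG finding categories may mean only the investigator's normal/abnormal assessment. Counting unscheduled interval values against cut-points could then be seen as summarising unscheduled quantitative data, which that section excludes. This is a fair reading, so a protocol conflict over Table 6 is not certain. On that reading, though, the investigator's assessment is itself given only by visit in SAP 8.6, so a whole-period summary is still missing.

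**Existing cover.** All ECGs are listed. SAP 8.6 also provides "A separate listing of data for subjects with postbaseline values of QTcF" of at least 500 msec or a rise above 60 msec. Clinically significant findings that meet the adverse event definition reach the treatment-emergent tables, and arrhythmia is an event of special interest: "The incidence of treatment-emergent AESIs will be summarized, overall (any AESI) and by system organ class and preferred term". With 110 subjects a hand count from the listings is possible. This cover is real, but a listing supplies neither a count nor a denominator. It also leaves PR, QRS, heart-rate and lower QTcF crossings that were not recorded as events.

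**Size and interpretation.** The stopping pattern is assumed. Without a control arm, and with a baseline that follows the randomized withdrawal period of Study 0170, an ever-crossed percentage is hard to interpret. It also rises with the number of ECGs taken. The missing control and the mixed baseline limit the by-visit counts as well. The dependence on the number of ECGs calls for a footnote.

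**Conclusion.** The concern holds for the visible text. As written, the SAP yields no per-subject count, with a denominator, of those who ever crossed a PR, QRS, heart-rate or lower QTcF threshold. It also keeps off-window Early Termination and unscheduled ECGs out of every summary of a primary safety endpoint.

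The firm figure is 84 of 189 days uncovered. The estimate of about 4 to 12 subjects losing their only post-baseline ECG from the summaries (8 to 24 under the narrower tabulation) depends on the assumed 20% to 60% stopping before Day 175, an even spread of stop days and an ECG on the stop day. Clustered stopping, as a sponsor termination could produce, would change it in either direction. Confidence is medium, mainly because of the redaction. Given the partial cover from listings and adverse event tables, this is a change that should be made rather than a flaw that undermines the study.

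**What to change.** In SAP 8.6, add to Table 6 a column for the worst value at any time post-baseline. Report n and % of safety-set subjects with at least one post-baseline ECG, each subject counted once. Use the triplicate average at each assessment, from scheduled, Early Termination, unscheduled and out-of-window ECGs. Then:

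- State it as an explicit exception to SAP 6, 6.3.5 and 6.3.6, for category counts only. By-visit means and changes stay as planned, which respects the protocol's rule on unscheduled quantitative data.
- Flag treatment-emergent cases using the Protocol 8.5.6 definition.
- Put the Normal/Borderline/Prolonged QTcF summary on the same basis.
- Keep the by-visit counts.

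If the Protocol 8.5 wording is read as covering the investigator's assessment only, Protocol 8.4 still allows the SAP to add this analysis.

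The cost is SAP wording, one table column and a little programming, with no new data. Symptom-prompted ECGs may raise the any-time counts, and a footnote should say so.
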